## 8.2 General Adverse Event Definitions

Following is a list of general AE definitions. For the purposes of this study, only SAEs, excluding elective procedures, as well as all AEs related to the operative site, should be reported.

### Adverse Event

An **AE** is any untoward medical occurrence in a clinical investigation subject, which changes the medical baseline of the subject. An AE can be an unfavorable and unintended sign, symptom or disease, whether or not related to the study device (AEs may also be referred to as complications). See Section 8.1, Reporting of Adverse Events, for the AE reporting requirements for this study.

### Anticipated Adverse Event

An **anticipated AE** is an AE, of which the nature, severity or degree of incidence is known and identified in applicable product labeling, published literature or study protocol. The list of anticipated events is provided in Section 12, Risk/Benefit Assessment.

### CONFIDENTIAL

### Serious Adverse Event

A SAE meets one or more of the following definitions:

- Resulted in in-patient hospitalization
- Resulted in prolonged existing hospitalization
- Resulted in persistent or significant disability/incapacity
- Resulted in permanent impairment of a body function or permanent damage to a body structure
- Necessitated medical or surgical intervention to preclude permanent impairment of a body function or permanent damage to a body structure
- Was a life-threatening situation
- Resulted in patient death

Elective procedures meeting the definition of a SAE do not need to be reported as AEs according to this study protocol.

### Adverse Device Effect

An **adverse device effect** (ADE) is a negative change in the subject's health that may have been caused by, or associated with, the use of the device.

### Unanticipated Adverse Device Effect

An **unanticipated adverse device effect** (UADE) is any serious adverse effect on health, safety or any life-threatening problem or death caused by, or associated with, a device if that effect is a problem or death not previously identified in nature, severity or degree of incidence, or any other unanticipated serious problem associated with a device and related to the rights, safety or welfare of subjects.

## 8.3 Study Sponsor Fax Notification by Investigator

Of reportable AEs, certain events must be submitted to Stryker within 24 hours for timely notification:

### Adverse events that require time sensitive reporting:

An adverse event should be reported to the study sponsor (CSM or CSA) either by telephone/fax/email within 24 hours of the site's becoming aware of the event if any of the following apply:

### CONFIDENTIAL

- The AE is considered by the investigator to be device related or if the investigator is uncertain regarding the device related assessment;
- The AE required a reoperation of the study knee or a revision of any study knee components.

An AE CRF must be completed by the investigator and submitted to Stryker within 24 hours. The investigator will keep a copy of this AE CRF on file at the study center and submit the hard copy as per CRF data submission procedures. If a SAE occurs, the de-identified source documentation must be submitted within 24 hours of the investigative center's SAE awareness. These reports will be evaluated by Stryker to determine if a Product Experience Report (PER) is required. Report SAEs to:

[name]	[name]
[contact]	[contact]
[contact]	[contact]
[contact]	[contact]

It is recommended that all other reportable adverse events are reported on eCRFs and submitted to Stryker within 2 weeks.

At the time of the initial report, the following information should be provided:

Subject number	Whether study treatment was
A description of the event	discontinued
Date of onset	
 
Investigator assessment of the
 

Current status	association between the event and
	the study treatment

### 8.3.1 Ethics Committee/Institutional Review Board Notification by Investigator

Reports of AEs (including follow-up information) must be submitted to the Ethics Committee (EC) or Institutional Review Board (IRB) according to their specific requirements. Copies of each report and documentation of EC/IRB notification and receipt will be kept with the investigator's study files.

CONFIDENTIAL

## 8.4 Recording of Adverse Events

All protocol defined AEs occurring during the study period must be recorded; this includes events that occur between visit intervals. The clinical course of each event should be followed until resolution or stabilization.

## 8.5 Medical Monitoring

It is the responsibility of the investigator to oversee the safety of the study at his/her center. This safety monitoring will include careful assessment and appropriate reporting of AEs, as noted above. Stryker will conduct formal investigations via the Product Surveillance Department of those AEs which are submitted through our PER System.

# 9 Statistical Plan

## 9.1 Efficacy

## 9.1.1 Primary Efficacy Parameters

The primary efficacy parameters will be total KSS, KSS pain score and KSS functional score, recorded at 2 years postoperative.

## 9.1.2 Secondary Efficacy Parameters

The secondary efficacy parameters will include:

- KSS pain and function score changes from preoperative at 1, 2 and 5-year visits
- SF-36 changes from preoperative at 1, 2 and 5-year visits
- KOOS changes from preoperative at 1, 2 and 5-year visits
- HSS Patella Score changes from preoperative at 1, 2 and 5-year visits
- LEAS score changes from preoperative at 1, 2 and 5-year visits

## 9.1.3 Primary Efficacy Hypothesis

For the primary efficacy hypothesis,  $H_0$ , the total KSS change from preoperative to 2 years postoperative will be less than or equal to  $\delta$ . The alternative hypothesis,  $H_{1a}$ , will be that the total KSS change from preoperative to 2 years postoperative is greater than  $\delta$ . When  $\delta$ =63 (see explanation in Section 9.4.2, Sample Size Calculation), the hypothesis will test for non-inferiority. When  $\delta$ =70, the hypothesis will test for superiority.

 $\textbf{H_{0}:} \ \mu_{\text{2-year}} \textbf{ - } \mu_{\text{preop}} \leq \delta$ 

Ha:  $\mu_{2-year}$  -  $\mu_{preop}$  >  $\delta$ 

### CONFIDENTIAL

## 9.1.4 Primary Efficacy Analysis

A one-sided 95% confidence interval of the total KSS change from preoperative to 2 years postoperative (2 years - preoperative) will be computed at 2 years postoperative. For the non-inferiority comparison, the lower bound of this confidence interval will be compared with 63. For the superiority comparison, the lower bound of this confidence interval will be interval will be compared with 70.

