### **Clinical Outcome**

Clinical outcomes will be evaluated via the total KSS, including pain, motion and function, preoperatively and at the 6-week, 1, 2 and 5-year visits.

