## 7.3 6-week Visit

During the 6-week visit (± 2 weeks), the following evaluations will be collected: KSS, AP, ML and Merchant (30° of flexion) radiographs.

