## 7.5 Annual Follow-up Visits

Clinical data will be collected via office visit by the investigator at the following annual postoperative intervals: 1-year, 2-year and 5-year. Tools for postoperative evaluation will be the KSS, AP, ML and Merchant (30° of flexion) radiographs.

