## 9.3 Missing Data

No missing data will be imputed for the primary analysis and secondary analyses.

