### 9.4.2 Sample Size Calculation

A total of 181 cases implanted with the Triathlon TS Total Knee System will be enrolled in the study. The mean total KSS improvement expected, as compared from preoperative to 2 years postoperative, is 70 points. It is assumed that the mean total KSS improvement from preoperative to 2 years postoperative for cases implanted with the Triathlon TS Total Knee System will be comparable to the expected rates (not 10% or 7 points worse), above 63 points. Given a standard deviation of 35 for the improvement in scores, 80% power, and a one-sided 0.05 alpha level to test the 10% (7 points) non-inferiority hypothesis, a sample size of 154 subjects will be required to meet the primary efficacy objective. By factoring in a 15% lost to follow-up rate within 2 years, a total enrollment of 181 subjects will be needed.

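### The primary KSS result uses only cases scored at 2 years, so it is biased if loss depends on earlier KSS, which is collected but not used

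*Combined protocol and SAP*

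**What the plan says.** The primary analysis in Section 9.1.4 is one sentence on estimation: "A one-sided 95% confidence interval of the total KSS change from preoperative to 2 years postoperative (2 years - preoperative) will be computed". The lower bound is then compared with 63 for non-inferiority and with 70 for superiority. Section 9.3 adds: "No missing data will be imputed for the primary analysis and secondary analyses". No repeated-measures model and no sensitivity analysis for missing scores appears in Section 9.

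On loss, Section 9.4.2 says: "By factoring in a 15% lost to follow-up rate within 2 years, a total enrollment of 181 subjects will be needed".

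On what is measured, Section 2.1.2 (Clinical Outcome) has total KSS evaluated "preoperatively and at the 6-week, 1, 2 and 5-year visits". Section 7.3 confirms the 6-week score ("the following evaluations will be collected: KSS, AP, ML"), and Section 7.5 the later ones: "Clinical data will be collected via office visit by the investigator at the following annual postoperative intervals: 1-year, 2-year and 5-year". The Evaluation Schedule agrees.

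Two further rules bear on the point. Section 11.6 lists a missing primary endpoint among the protocol deviations. Section 9.4.4.4 removes from the efficacy population any subject with a deviation that could affect outcome.

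**The concern.** The plan never calls its analysis complete-case, but Sections 9.1.4 and 9.3 together make it one. A case with no 2-year KSS has no change score, nothing stands in for it, and no other visit enters the estimate. The mean of the remaining cases estimates the mean for all implanted cases only if loss is unrelated to outcome.

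This matters more here than in a two-arm trial. There is one arm and the comparison is with fixed numbers, so there is no control group in which similar losses could partly cancel. Any bias in the mean moves the bound directly toward or away from 63 and 70, and the margin is only 7 points. Raising enrolment to 181 protects the number of scores analysed. It does nothing about which cases supply them.

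**Working it through.** **Inputs from Section 9.4.2.** "Given a standard deviation of 35 for the improvement in scores, 80% power, and a one-sided 0.05 alpha level"; expected mean change 70, threshold 63, margin 7; 154 evaluable, 181 enrolled, 15% loss.

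**Assumptions, not in the documents.** ρ is the correlation between an earlier KSS change and the 2-year change. D is the gap in that earlier change between retained and lost cases. Both changes have SD 35, and loss is related to the 2-year change only through the earlier score.

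**1. The plan's own figures.** n = (35 × (1.645 + 0.842) / 7)² = 154.6, stated as 154. Then 154 / 0.85 = 181.2, stated as 181. Power at 154 is 79.9% by the normal formula and 79.6% by the noncentral t. The figures reproduce as a one-sample mean on 154 cases with a 2-year score, which fits the completers-only reading.

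**2. Base quantities.** SE = 35 / √154 = 2.82. Lost cases = 181 − 154 = 27, a share m = 27 / 181 = 0.149.

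**3. Bias and error rate.** Bias of the completer mean = m × ρ × D. One-sided error at a true mean of 63 = Φ(bias / SE − 1.645). For D = 10 and ρ = 0.7: bias = 0.149 × 0.7 × 10 = 1.04, which is 15% of the margin; error = Φ(1.04 / 2.82 − 1.645) = 10.1%.

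| Lost cases lower earlier by (D) | ρ = 0.5: bias, error | ρ = 0.7: bias, error | ρ = 0.8: bias, error |
|---|---|---|---|
| 5 points | 0.37, 6.5% | 0.52, 7.2% | 0.60, 7.6% |
| 10 points | 0.75, 8.4% | 1.04, 10.1% | 1.19, 11.1% |
| 20 points | 1.49, 13.2% | 2.09, 18.3% | 2.39, 21.2% |

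**4. The opposite direction.** If lost cases scored 10 points higher earlier, the completer mean is too low by the same amounts. Power at a true mean of 70 then falls from 79.9% to 71.7%, 68.0% and 66.1% for ρ = 0.5, 0.7 and 0.8.

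**5. Precision.** With N₁ cases having an earlier score, the variance of a likelihood estimate is 35² × [(1 − ρ²) / 154 + ρ² / N₁]. For ρ = 0.7 and N₁ = 181, SE = 2.72 and power = Φ(7 / 2.72 − 1.645) = 82.5%. Over ρ = 0.3 to 0.8, power is 80.3% to 83.3% if all 27 lost cases have an earlier score, and 80.1% to 81.7% if half do. With no loss at all (n = 181) it would be 85.2%.

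**6. Simulation check.** This used 20,000 trials of 181 cases, ρ = 0.7, a true mean of 63, and about 15% loss depending on the 1-year score (gap about 17 points). The completer mean was biased by +1.7 with error 15.1%. The likelihood estimate using the 1-year score had bias of about −0.03 and error 4.9%. When loss did not depend on score, both methods had error of 5.2%.

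**The case against.** The strongest reply is that nothing in the documents says poor performers leave. The one cause of attrition that Section 15.3 names is loss of health insurance, which has no stated link to score. The plan also works to limit loss: three recorded calls and a certified letter before a case is declared lost (Section 10.3), an optional retention programme (Sections 12.5 and 15.3), and case-by-case reimbursement of visits (Section 15.3). This stands as far as it goes. A reader might infer that the result is tilted in favour of the device, and the documents do not support that. The bias is conditional and its direction is unknown. But measures that reduce loss do not correct for the 15% still expected, and the plan neither models nor tests it.

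A reader might also infer that every lost case has both a 6-week and a 1-year score. That does not follow: a case lost before 1 year has at most the 6-week score, and the documents do not say when losses occur.

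Nor is the study left short of power. Enrolment of 181 already allows for the loss, so the gain in precision is a small extra.

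Finally, error rates near 20% are an upper-end reading. A gap of 15 points in the unobserved 2-year change gives a bias of 0.15 × 15 = 2.25 and an error of 19.8%. To arise through the earlier score it needs an earlier gap of 15 / 0.7 = 21 points, or 15 / 0.5 = 30 points.

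**Conclusion.** The point holds as a conditional risk of bias in the primary estimate, and the plan already collects data that would reduce it. For earlier-score gaps of 5 to 10 points the one-sided error is roughly 6.5% to 11% instead of 5%. These sizes rest on the assumed gap, correlation and equal SDs, so they show scale and do not predict the result.

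Section 9.3 does not stand in the way. A likelihood model imputes nothing, so it is permitted but unspecified. The model removes bias only where loss depends on observed scores, which is why it needs a sensitivity analysis beside it. A pre-specified supportive model would meet part of the concern. Making it primary is better, because the bound compared with 63 and 70 is the one exposed to the bias. The change is worth making, but the point does not by itself invalidate the design.

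**What to change.** - **Section 9.1.4:** estimate the mean 2-year change and its one-sided 95% lower bound from a likelihood-based repeated-measures model of total KSS (preoperative, 6 weeks, 1 year, 2 years; unstructured covariance). Compare that bound with 63 and 70. Keep the completer mean as a supportive analysis.
- **Section 9.4.4.4:** state that an unavailable 2-year KSS alone does not censor a case's earlier scores. Otherwise, read with Section 11.6, lost cases could be removed before any model is fitted.
- **Sensitivity analysis:** lower the assumed 2-year change of lost cases by a range of fixed amounts. With 27 of 181 lost, each 10 points lowers the overall mean by about 1.5 (0.149 × 10).
- **Revision and death:** do not treat cases ended for these reasons (Section 10.3) as ordinary loss in this model. State a separate analysis rule for them.
- **Secondary scores:** use the visits at which each is collected, namely 6 months, 1, 2 and 5 years for SF-36, KOOS, HSS Patella Score and LEAS, and 6 weeks, 1, 2 and 5 years for the KSS components.

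The cost is SAP wording and a mixed-model run in the SAS software already planned (Section 9.4.1), with no new visits or data. The downside is slightly more analysis work and reliance on loss depending only on observed scores.

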## 9.1.5 Secondary Efficacy Analysis

A two-sided 0.05 alpha level will be used.

For the secondary efficacy parameters when data is available, comparisons of numerical variables between subgroups (e.g. JL groups) will be made by a paired t-test or Wilcoxon rank sum test; comparisons of categorical variables between subgroups will be made by a Fisher's exact test.

One-way analysis of covariance (ANCOVA) may be used as a supportive analysis to determine if the score change from preoperative is significantly different between the subgroups after adjusting the preoperative covariates (e.g. age, gender, BMI), if appropriate.

The mean score improvement from the preoperative time point within the Triathlon® TS Outcomes Study will be summarized in tables at each nominal visit. A p-value will be presented to determine if the mean score improvement from the preoperative time point is non-zero, if appropriate.

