## Primary:

	A one-sided 95% confidence interval of the total KSS change from preoperative to 2 years postoperative (2 years - preoperative) will be computed at 2 years postoperative. For the non-inferiority comparison, the lower bound of this confidence interval will be compared with 63 points (10% worse than the expected improvement). For the superiority comparison, the lower bound of this confidence interval will be compared with 70 points (the expected improvement).
Statistical Methodology	Secondary:
	An independent group t-test or a nonparametric test will be used to
	compare the secondary numerical parameters (e.g. KSS, HSS, KOOS)
	between the JL restoration subgroups at 1, 2 and 5 years
	postoperative; and a Chi-square test or Fisher's exact test will be used
	to compare the secondary categorical parameters (e.g. postoperative
	stability, anterior knee pain and functional performance) between the
	subgroups. In addition, a paired t-test or Wilcoxon rank sum test will be
	used to compare the change in outcomes other than the KSS from
	preoperative to 1, 2 and 5 years postoperative within the Triathlon TS
	Total Knee System group. The radiographic stability rates, adverse
	event (AE) rates and revision rates with 95% confidence intervals will
	be presented in tables.

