### CONFIDENTIAL

Page 8

In addition to improving patient outcomes, one of the challenges in revision TKR is restoration of the JL. Improper positioning of the JL has been shown to lead not only to instability but also to an increased incidence of anterior knee pain and decreased flexion. Malposition may also lead to patellar infera and posterior soft tissue impingement by the femoral component. Mason et al., in a study of six cadaver knees, investigated four anatomic landmarks for locating the JL during revision knee surgery – the medial femoral epicondyle (ME), the fibular head (FH), the tibial tubercle (TT), and the inferior pole of the patella (IPP). In this study, the distance between the ME and the JL showed very small patient-to-patient variability. As a result, it was concluded that the ME is a reliable and reproducible landmark for JL measurements.

Additionally, Mahoney and Kinsey retrospectively reviewed JL restoration and clinical outcomes in 22 consecutive femur revision cases. The authors used specialized instruments and were able to restore JL to within 2 mm of anatomic position in 12 of the 22 knees. Flexion and extension gap balancing and ME referencing were reliable methods of measuring and achieving proper position of the JL.

As a secondary objective, this outcomes study of the Triathlon TS Total Knee System will also examine the effect of JL restoration on a subset of revision TKR cases with a non-replaced contralateral knee at the time of study surgery. The effect will be evaluated by comparing between cases with JL restoration > 5 mm and cases with JL restoration  $\leq$  5 mm. As little as 5 mm of displacement from the JL can cause laxity in midflexion or tightness, even in a gap-balanced knee.

For all cases, at the time of study surgery, surgeons will intraoperatively measure, in millimeters, the distance between the ME and the JL in full extension and in 90° of flexion. This measurement will be taken before removal of the previous implants as well as after implantation of the final Triathlon® TS Total Knee System.

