#### CONFIDENTIAL

The protocol for measuring JL is referenced in Appendix A. Stability, anterior knee pain and the functional component of the KSS will be evaluated with respect to JL.

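### Section 9.1.5 names a paired t-test for independent joint-line groups, contradicting the synopsis, and the synopsis names the rank-sum test for within-case change

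*Combined protocol and SAP*

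**What the plan says.** Section 9.1.5 (Secondary Efficacy Analysis) sets a two-sided 0.05 level and states that "comparisons of numerical variables between subgroups (e.g. JL groups) will be made by a paired t-test or Wilcoxon rank sum test". For change from baseline it says only that "A p-value will be presented to determine if the mean score improvement from the preoperative time point is non-zero", without naming a test.

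The Statistical Methodology row of the synopsis covers the same two tasks differently:

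- Between JL groups, for numerical parameters: "An independent group t-test or a nonparametric test will be used to" compare them "between the JL restoration subgroups at 1, 2 and 5 years".
- Within the single Triathlon TS group, for change from preoperative in outcomes other than the KSS: "a paired t-test or Wilcoxon rank sum test will be" used.

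Section 1.1 (Background) defines the JL analysis as "comparing between cases with JL restoration > 5 mm and cases with JL restoration" of 5 mm or less, in the subset whose contralateral knee had not been replaced at study surgery. The same section adds that "the functional component of the KSS will be evaluated with respect to JL".

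**The concern.** A paired test needs a one-to-one link between observations in the two groups. The two JL groups are separate sets of cases, and the plan describes no matching. The two places in the document therefore give conflicting instructions for the first-listed secondary objective, and the inapplicable one sits in the statistical section, which an analyst would follow.

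Within cases the error is reversed. Preoperative and postoperative scores come from the same case, and rank-sum treats them as independent samples. If an analyst judged the scores too skewed for a t-test and took the only nonparametric option listed, the pairing would be thrown away. That could affect SF-36, KOOS, HSS Patella Score and LEAS changes at 1, 2 and 5 years. What is at stake is lost power for modest changes, and an analysis that is not properly prespecified. There is no added risk of false-positive claims when the pre/post correlation is positive.

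**Working it through.** **1. The instructions side by side.**

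| Task | Data structure | Synopsis | Section 9.1.5 | Suitable tests |
|---|---|---|---|---|
| JL > 5 mm vs ≤ 5 mm, numerical | Two unmatched groups | Independent-group t, or unspecified nonparametric | Paired t, or rank-sum | Independent-group t, or rank-sum |
| Change from preoperative | Same cases measured twice | Paired t, or rank-sum | p-value promised, no test named | Paired t, or signed-rank |

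Each place lists one suitable and one unsuitable test. The pair of tests in 9.1.5 for the between-group task is the pair the synopsis uses for the within-case task, which suggests a drafting slip.

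**2. Could the JL groups be paired some other way?** No. No matching is described, and restricting the subset to cases with a non-replaced contralateral knee means two study knees of one patient are not paired by design. A trial run of a paired t-test on groups of 30 and 40 returned an error. With equal group sizes any pairing would be arbitrary.

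**3. The plan's own figure.** Section 9.4.2 uses SD 35, margin 7, one-sided 0.05 and 80% power:

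n = [35 × (1.64485 + 0.84162) / 7]² = (5 × 2.48647)² = 154.56, stated as 154. Enrollment: 154 / 0.85 = 181.2, stated as 181.

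This reproduces to rounding and does not depend on the secondary test names.

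**4. Size of the rank-sum slip.** Inputs:

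- n = 154 and change SD 35, both from 9.4.2. The SD is for total KSS and is borrowed, because none is given for the secondary scores.
- Two-sided 0.05, from 9.1.5.
- Pre/post correlation ρ is not given; 0.3, 0.5 and 0.7 are assumed.

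With equal variances the score SD is 35/√(2(1−ρ)), which is 29.6, 35.0 and 45.2. Each setting used 20,000 simulated data sets of bivariate-normal pairs.

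| True change | Test | ρ = 0.3 | ρ = 0.5 | ρ = 0.7 |
|---|---|---|---|---|
| 0 | rank-sum | 0.020 | 0.007 | 0.0006 |
| 0 | signed-rank | 0.051 | 0.051 | 0.046 |
| 7 points (0.2 SD) | rank-sum | 0.52 | 0.36 | 0.13 |
| 7 points | signed-rank | 0.67 | 0.68 | 0.67 |
| 7 points | paired t | 0.69 | 0.70 | 0.69 |
| 10 points | rank-sum | 0.87 | 0.75 | 0.45 |
| 10 points | signed-rank | 0.93 | 0.93 | 0.93 |

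At ρ = 0 the two rank tests agree (0.050 and 0.049 with no change; 0.677 and 0.673 at 7 points), so the loss comes from ignoring the pairing.

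**5. Closed-form check of the type I error.** Rank-sum uses a variance for independent samples, which is too large by the factor 1/(1−ρₛ), where ρₛ is the rank correlation. For normal data ρₛ = (6/π)·arcsin(ρ/2), giving 0.288, 0.483 and 0.683. The effective critical value is 1.96/√(1−ρₛ) = 2.32, 2.72 and 3.48, with two-sided tail areas 0.020, 0.006 and 0.0005. These agree with the simulation.

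**6. Larger changes.** With 4,000 data sets per setting, rank-sum power at 15 points (0.43 SD) is 0.998, 0.990 and 0.943 at ρ = 0.3, 0.5 and 0.7. At 20 points (0.57 SD) it is at least 0.999 throughout.

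**The case against.** The strongest reply is that these are naming slips that would do little harm.

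- **The JL error cannot give a wrong result.** A paired t-test fails on unmatched groups, and rank-sum satisfies both places. This stands, and it is why no numerical effect is claimed. It does not settle which t-test is prespecified.
- **Section 9.1.5 asks whether mean improvement is non-zero.** That is a one-sample question on change scores, on which a two-sample rank-sum test cannot be run, so the natural reading is the paired t-test that the synopsis lists first. This is a fair reading. But 9.1.5 names no test, and the only nonparametric option written down for within-case change is the wrong one.
- **The power figures are weakly anchored.** The SD belongs to total KSS, while the synopsis limits this within-case test to outcomes other than the KSS. The 7-point change is the primary margin, not an expected secondary effect. The loss is concentrated at about 0.2 to 0.3 SD, and the error is conservative. All of this stands: the figures illustrate direction and order of size and do not forecast the loss for any particular score.
- **Renaming the t-test leaves a larger JL problem.** Section 2.1.2 frames the JL expectation as non-inferiority, which a two-sided difference test does not address. That is a separate issue and does not weaken this correction.

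**Conclusion.** The point holds and should be fixed. The unsuitability of the paired t-test between JL groups, its conflict with the synopsis, and the unsuitability of rank-sum for within-case change all follow from the text and the data structure, without any assumption. Only the size of the power loss rests on assumptions: the borrowed SD of 35, normal scores with equal variances, and pre/post correlations of 0.3 to 0.7. Under these, rank-sum loses roughly 15 to 54 percentage points of power for a 7-point change (0.67 − 0.52 = 0.15; 0.67 − 0.13 = 0.54) and very little beyond about 15 points. Only secondary numerical analyses are involved.

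**What to change.** - **Section 9.1.5, between JL groups:** replace the paired t-test with an independent two-sample t-test, keeping rank-sum as the nonparametric alternative. This agrees with the synopsis.
- **Synopsis, within-case change:** replace the Wilcoxon rank-sum test with the Wilcoxon signed-rank test, keeping the paired t-test.
- **Section 9.1.5, p-value for non-zero improvement:** name the paired t-test or the signed-rank test.
- **Optional:** the supportive ANCOVA is described as "adjusting the preoperative covariates (e.g. age, gender, BMI), if appropriate". The list is only illustrative; adding the preoperative score to it would be sensible, and the ANCOVA can stay supportive.

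The cost is a few words in two places. No new data are needed and the sample size does not change. Making the correction before the secondary data are analyzed avoids having to report it as an unplanned deviation.

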## 5.2 Randomization

This study will enroll under a non-randomized study design.

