### CONFIDENTIAL

# 7 Evaluations

## 7.1 Preoperative Visit

During the preoperative visit, patients that are possible candidates for this study will be screened to determine if they meet the inclusion/exclusion criteria. If the patient is a candidate, the investigator will propose participation in the study to the patient, according to GCP guidelines. Patients must sign an IRB approved study consent form prior to participating in any study related activities. Consent must be obtained within four months of surgery.

Once the subject has been consented, preoperative data will be collected including: demographics, medical history, KSS, AP, ML and Merchant (30° of flexion) radiographs, SF-36, KOOS, HSS Patella Score, and LEAS. All information collected preoperatively will be used to quantify the sample population and compare postoperative progress.

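### The joint-line comparison of numerical scores is unadjusted, and the optional ANCOVA does not name the preoperative score as a covariate

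*Combined protocol and SAP*

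**What the plan says.** Section 9.1.5 sets the main analysis for the joint-line groups: "comparisons of numerical variables between subgroups (e.g. JL groups) will be made by a paired t-test or Wilcoxon rank sum test". The synopsis (Statistical Methodology, secondary) describes the same comparison differently: "An independent group t-test or a nonparametric test will be used to" compare the numerical parameters. Neither version adjusts for anything. The conflict between a paired and an independent t-test is a separate matter; correcting the test name would leave the present point unchanged.

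Adjustment appears only in the next paragraph of Section 9.1.5: "One-way analysis of covariance (ANCOVA) may be used as a supportive analysis", and its purpose is "to determine if the score change from preoperative is significantly different between the subgroups". The sentence ends "between the subgroups after adjusting the preoperative covariates (e.g. age, gender, BMI), if appropriate", so age, gender and BMI are given as examples. The synopsis does not mention ANCOVA.

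On the groups, Section 5.2 states: "This study will enroll under a non-randomized study design". Section 1.1 restricts the joint-line analysis to "a subset of revision TKR cases with a non-replaced contralateral knee at the time of study surgery" and splits cases at 5 mm. No size, split or power is given for that subset.

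On the available data, Section 7.1 states: "Once the subject has been consented, preoperative data will be collected including: demographics, medical history, KSS", and goes on to list SF-36, KOOS, HSS Patella Score and LEAS. The Evaluation Schedule agrees. Every numerical instrument therefore has a preoperative value.

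**The concern.** Group membership depends on where the joint line ended up after surgery, so preoperative balance cannot be presumed. It is plausible, though the documents do not say so, that harder revisions have both lower preoperative scores and more joint-line displacement.

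If the groups do start at different levels, an unadjusted contrast mixes that starting difference with any effect of joint-line position. Section 2.1.2 expects the group above 5 mm to be non-inferior to the other. A shift of a few points in either direction could therefore support or undermine that expectation for reasons unrelated to the joint line.

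The preoperative score is usually one of the strongest predictors of the later score, and leaving it out also costs precision. That matters in a subset whose size is not stated. Because the ANCOVA is optional and its list is open, the plan does not fix in advance whether adjustment will be made or for what.

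**Working it through.** **Figures in the plan.** The joint-line comparison has none. The nearest is the primary sample size in Section 9.4.2: SD of change 35, margin 7, one-sided 0.05, 80% power. This gives (35 × 2.4865 / 7)² ≈ 154.6 against 154 stated, and 154 / 0.85 = 181.2 against 181 stated. Both reproduce to within rounding and are not in question. The SD of 35 for change in total KSS is used below for scale.

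**Which outcome is compared.** Section 9.1.2 defines the secondary parameters as changes from preoperative. The synopsis compares parameters such as KSS, HSS and KOOS between joint-line groups at 1, 2 and 5 years, and speaks of change only for the separate within-group analysis. Both readings are therefore worked through.

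**Assumptions, none of them in the documents.** Equal pre and post variance σ²; pre-post correlation r from 0.3 to 0.6; one group starts d = 10 points lower; the groups have equal expected outcomes given baseline.

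**Shift in the unadjusted contrast** for the lower-starting group:
- Postoperative score: −r × d.
- Change: −r × d + d = (1 − r) × d.

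**Variance after adjusting for the preoperative score.** The residual variance is σ²(1 − r²).
- Relative to change, whose variance is 2σ²(1 − r), the ratio is (1 + r)/2.
- Relative to the postoperative score, whose variance is σ², the ratio is 1 − r².

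| | r = 0.3 | r = 0.6 |
|---|---|---|
| Shift, change contrast | +7 | +4 |
| Shift, postoperative contrast | −3 | −6 |
| Variance ratio against change | 0.65 | 0.80 |
| Variance ratio against postoperative score | 0.91 | 0.64 |

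Taking square roots, the standard error falls by 19% to 11% against the change analysis (√0.65 = 0.81, √0.80 = 0.89). Against the postoperative analysis it falls by 5% to 20% (√0.91 = 0.95, √0.64 = 0.80). With a change SD of 35, the residual SD becomes 28.2 at r = 0.3 and 31.3 at r = 0.6.

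**Check by simulation** (change score, 77 cases split 23/54, 10-point imbalance, no group effect given baseline, 4,000 runs per setting, nominal two-sided 5%):
- r = 0.3: ANCOVA with age, gender and BMI only gave a mean spurious difference of 7.2 points in size and rejected in 13.1% of runs. Adding the preoperative score gave 0.2 points and 5.0%.
- r = 0.5: 5.0 points and 9.0%, against 0.1 points and 5.4%.

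The simulated age, gender and BMI were unrelated to outcome, so they could remove none of the shift. The simulation confirms the algebra under its assumptions. It does not test whether those assumptions hold in this study.

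**The case against.** Several points on the other side stand.

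- A reader might infer that the plan excludes the preoperative score from the ANCOVA. It does not. The covariates are introduced as examples, and a preoperative score is a preoperative covariate. The score is unnamed, not ruled out.
- A reader might infer that regression to the mean will hide a harm of joint-line displacement. The documents do not support a direction. If change is compared, a lower-starting group is flattered; if postoperative score is compared, it is penalised. Nor do the documents show which group starts lower, or that they differ at all.
- The shifts hold only if the groups would have equal expected outcomes given baseline. The groups are formed by surgical result, not by selection on a noisy preoperative score. If the preoperative difference reflects a stable difference in severity, each group may regress towards its own mean. Change-score and ANCOVA estimates can then legitimately differ, and ANCOVA is not automatically the less biased.
- The reach is narrow. The synopsis treats stability, anterior knee pain and functional performance as categorical outcomes with Chi-square or Fisher's exact tests, which are untouched. What remains is the KSS functional component, which Section 1.1 ties to the joint line, and the other numerical scores.
- If one joint-line group is small, a long list of compulsory covariates could strain the model.

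These points limit the claim about bias and argue for keeping the unadjusted result in view. They do not remove the case for deciding the model in advance and naming the strongest available covariate. An optional analysis with an open list pre-specifies neither.

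**Conclusion.** The point holds as a gap in pre-specification for the numerical joint-line comparisons. The main test is unadjusted in non-randomised groups, adjustment is optional, and the preoperative score is not named although it is collected for every instrument.

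The size is conditional on the correlation and imbalance assumed in the working and on comparability given baseline. The shifts of 4 to 7 points in one direction or 3 to 6 in the other should be read as what could happen, not as a demonstrated bias. The precision gain does not need a preoperative imbalance, but it too depends on the assumed correlation and on equal variances.

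It would be wrong to conclude that baseline adjustment makes the groups comparable: confounding by reason for revision, center or other factors would remain. It would also be wrong to carry the point over to the primary objective. The single-arm test against 63 and 70 and the 154/181 figures are unaffected.

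**What to change.** In Section 9.1.5, pre-specify ANCOVA for the numerical joint-line comparisons (KSS, KOOS, HSS Patella Score, LEAS, SF-36). Make the preoperative value of the same score a required covariate, and add age, gender and BMI where group sizes allow. Report the unadjusted two-sample comparison alongside it and state whether that comparison uses change or postoperative score. With the preoperative score in the model, the estimated group difference is the same for either outcome, so the ambiguity no longer affects the adjusted result. Bring the synopsis into line, and acknowledge that other confounding is not removed.

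The cost is small. No new data, visits or cases are needed. The model spends one degree of freedom on the preoperative score and up to three more on age, gender and BMI. If postoperative scores were to be compared, cases without a preoperative score would be lost from the adjusted analysis, since Section 9.3 rules out imputation. If change was intended, those cases are already lost.
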